Coordinating Investigator:	[REDACTED] [REDACTED] ext [REDACTED] 24-hour telephone [REDACTED] Email: [REDACTED]
Test sites	[REDACTED]
Laboratory sites	[REDACTED] [REDACTED]
Area of investigation	COVID-19
Justification for the programme	In order to have a correct diagnosis for individuals infected with SARS-CoV-2, reliable diagnostic tools must be identified, selected and regularly used. All results must be interpreted in relation to medical history and clinical evidence. RT-qPCR is the standard for identifying SARS-CoV-2 infection using viral RNA detection, generally with medical staff taking nasopharyngeal samples. This is considered to be an established procedure and is expected to provide reliable results; however, it has been found that the procedure depends on participant cooperation and staff experience. Compared to the previous technique, self-sampling is not considered optimal and may produce false-negative results due to the complex collection techniques and confounding human factors. In some cases it is difficult or impossible to obtain suitable samples. Self-sampling can lead to a lower risk of spreading the virus, as no visits to special centres are required. Furthermore, the biosafety level and risk of infections of medical staff when taking swab samples are reduced significantly.
Objective of the programme	The objective of the comparison is to demonstrate that saliva collection with Salivette® Cortisol is as reliable as the use of throat swabs in sampling viral RNA for RT-qPCR and identifying SARS-CoV-2 infections. PCR for RNA detection of SARS-CoV-2 in throat swab samples and saliva samples collected with Salivette® Cortisol BI internal laboratories Certified external laboratories

Protected confidential information ©2020 Boehringer Ingelheim International GmbH or one or more of its affiliated companies

Programme design	Parallel tests of different sample matrices
Number of participants	Total number: minimum of 20 and up to 80 participants who are positive for SARS-CoV-2
Main inclusion criteria for the pilot phase	COVID-19 diagnosis confirmed by PCR (within the past 5 days)
In vitro diagnosis	
• Kylt® for detection/confirmation of SARS-CoV-2 (PCR) [REDACTED]• cobas® SARS-CoV-2 (PCR) test [REDACTED]• TaqPath™ COVID-19 CE-IVD RT-PCR kit [REDACTED]
Day of the test	One single sample is planned
Statistical methods	Descriptive statistics directly comparing the test results

TABLE OF CONTENS

TEST PROTOCOL	1

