1.4 RISK-BENEFIT ASSESSMENT

The Salivette® Cortisol device, which is placed in the mouth and gently chewed for approximately 60 seconds, is considered to be very low risk. Its taste may be considered unpleasant. It is handled by the participant and, as such, there is no additional risk expected for the medical staff. During the tests, everyone wears masks in the rooms while the swab samples are taken, and the medical staff are protected with FFP2 masks, protective clothing and double gloves. Sampling with Salivette® Cortisol can be performed on-site. The layout of the room will follow the general distancing and hygiene measures in place, and surfaces will be cleaned and disinfected in line with procedure after each participant leaves. The risk of harm, such as sequelae due to the medical procedure, and the risk of infection of all participants, including the occupational health care team, was assessed before the tests and was considered highly unlikely.

There is recent evidence (Wyllie, AL et al. 2020. <https://doi.org/10.1101/2020.04.16.20067835doi>) that saliva sampling potentially produces more reliable results when compared to swab sampling.

Conclusions: It is considered necessary to establish sampling methods other than swab samples in order to reduce the biosafety risk and increase the flexibility of tests and their acceptance among potentially infected individuals, as taking swab samples is more invasive than collecting samples with Salivette® Cortisol. The sampling method established should allow for regular tests and be easy and well accepted by patients, while providing comparable results.

Risks and methods related to the medical procedure

There are some risks involved in the nasopharyngeal mucosa sampling procedure using swabs, such as mild bleeding of the nasal mucosa, pharyngeal pain after the sample is taken, sneezing, cough, and gag reflex when taking the pharyngeal mucosa sample. There are no known risks for patients related to the Salivette® Cortisol device, and even accidental ingestion of the device has not led to any adverse reactions being reported, as it is made of inert material and does not contain any active or reactive substances.

[figure not shown]
Sample taking with swab/Salivette® Cortisol

SARS-CoV-2 sampling:

The nasopharyngeal mucosa swab samples and those taken with the Salivette® Cortisol device will be collected in line with the SARS-CoV-2 biological sample collection standards in place at the Research Site.

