2. OBJECTIVES AND GOALS

2.1 MAIN OBJECTIVES AND PRIMARY GOALS

2.1.1 Main objectives

The main objective of the tests is to establish saliva collection with Salivette® Cortisol.

For PCR:

Real-time RT-PCR (██████████)	+/-
Real-time RT-PCR ██████████	+/-

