2.1.2 Main diagnosis for admission

Suspected or confirmed cases of SARS-CoV-2 infections (including COVID-19), confirmed with PCR within the past five days.

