2.1.3 Inclusion criteria

Only participants who meet the following criteria will be included in the programme:

1. Informed consent form signed and dated before any samples have been taken.
2. Suspected or confirmed SARS-CoV-2 infection by PCR within the past five days.
3. Male and/or female patients aged 18 years and over.

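### The summary promises to show that saliva is as reliable as throat swabs, but the plan is descriptive only and allows as few as 20 pairs

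*Combined protocol and SAP*

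**What the plan says.** The Objective row of the protocol summary reads: "The objective of the comparison is to demonstrate that saliva collection with Salivette® Cortisol is as reliable as the use of throat swabs". The Statistical methods row of the same table reads, in full, "Descriptive statistics directly comparing the test results". The Number of participants row gives a "minimum of 20 and up to 80 participants who are positive for SARS-CoV-2". Section 3 repeats the range of 20 to 80, says that no size was calculated, and describes the exercise as a general attempt at comparing the two sample types within a participant.

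The body is milder than the summary. Section 2.1.1 says "The main objective of the tests is to establish saliva collection with Salivette® Cortisol", with no comparator or criterion, and lists PCR results as positive or negative. The conclusions of section 1.4 ask for a method that should "be easy and well accepted by patients, while providing comparable results". The summary also refers to a pilot phase.

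The entry wording differs between places. The summary speaks of participants who are positive, with PCR confirmation in the past 5 days. Section 2.1.2 admits "Suspected or confirmed cases of SARS-CoV-2 infections (including COVID-19), confirmed with PCR within the past five days", and section 2.1.3 requires "Suspected or confirmed SARS-CoV-2 infection by PCR within the past five days".

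**The concern.** Demonstrating equal reliability is a confirmatory conclusion. It needs a stated measure of agreement or difference, an interval, and a rule for what result would count. The plan has none of these, so whoever writes the report must decide afterwards whether the observed agreement is good enough. If enrolment stops near 20, close agreement could be reported as equal reliability while a sizeable loss of detection remains compatible with the data.

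This matters for the intended use. The introduction looks towards sampling at home and testing as many people as possible, section 1.1 warns of infected people transmitting unwittingly, and the justification raises false negatives with self-sampling. Missed infections are therefore the error of most interest.

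**Working it through.** **Inputs from the documents.** A binary PCR result for each sample (section 2.1.1); pairing within participant (section 3); n from 20 to 80 (summary and section 3). There is no stated calculation to reproduce.

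**Assumptions, not from the documents.** Two-sided 95% intervals; illustrative margins of 10 and 5 percentage points; the discordance rates below; a 10% true loss as an example.

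**Notation.** b = pairs positive on saliva only, c = pairs positive on swab only. The difference is saliva minus swab positivity, (b − c)/n. Its lower limit comes from the paired score (Tango) method. With b = c = 0 that limit is −z²/(n + z²), with z² = 3.8415. The exact (Clopper-Pearson) lower limit for n of n positive is 0.025^(1/n).

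**Step 1: every same-day swab positive, so b = 0.**

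| Result | Exact lower limit, positive agreement | Paired-score lower limit |
|---|---|---|
| 20/20 | 0.025^(1/20) = 83.2% | −3.8415/23.8415 = −16.1 points |
| 19/20 | 75.1% | −23.6 points |
| 80/80 | 0.025^(1/80) = 95.5% | −3.8415/83.8415 = −4.6 points |
| 78/80 | 91.3% | −8.7 points |

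At 80 pairs, three saliva misses (77/80) give −10.5 points. At 20 pairs even the best possible result leaves a miss rate of 100 − 83.2 = 16.8% within the interval.

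**Step 2: chance of a misleading perfect result.** If saliva truly missed 10% of swab-positive participants, the probability of 20/20 is 0.9^20 = 0.122.

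**Step 3: some same-day swabs negative, so b can exceed 0.** This is possible because the qualifying PCR may be up to five days old. At n = 20 the lower limits are −11.9 points for (b, c) = (1, 0), −7.7 for (2, 0) and −19.9 for (1, 1). At n = 80 they are −9.9 for (7, 7) and −10.4 for (8, 8). So when the two methods look equal, or saliva looks worse, 20 pairs do not clear 10 points. At 80 pairs up to 7 discordant pairs each way do.

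**Step 4: chance that the lower limit clears the margin** when true detection is equal, by full enumeration of b and c.

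| Discordance each way | n = 20, 10 points | n = 80, 10 points | n = 80, 5 points |
|---|---|---|---|
| 2% | 4% | 91% | 38% |
| 5% | 11% | 70% | 23% |
| 10% | 13% | 49% | 16% |

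**Step 5: fewest pairs that clear a margin with no discordance.** For 10 points: n = 34 gives −3.8415/37.8415 = −10.15 and n = 35 gives −3.8415/38.8415 = −9.89, so 35. For 5 points: n = 72 gives −5.07 and n = 73 gives −4.999, so 73. These are thresholds for a perfect result, not planning sizes. For 80% power, the normal approximation n = ψ(1.960 + 0.842)²/margin², with ψ the total discordance, gives 79 pairs at 10 points with ψ = 10%, and 157 at 5 points even with ψ = 5%. The approximation is optimistic: the enumerated chance at 80 pairs with ψ = 10% is 70%.

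**The case against.** The strongest reply is that this is openly a pilot. The confirmatory wording is one sentence in the summary; section 2.1.1 speaks only of establishing the collection method, section 3 admits that no size was calculated, and the documents tie no treatment decision to the result. Descriptive statistics may also include confidence intervals. Much of this stands. It shows that a descriptive plan suits the milder objective, and it lowers the severity. It does not remove the mismatch: the summary sentence is the only statement of what the comparison should conclude, the rows concerned are not redacted, and no interval or rule is specified.

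It is also fair that the 10- and 5-point margins are illustrative. A 20-point margin would be cleared by 20/20, at −16.1. The margin-free result is the 83.2% lower limit.

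Three stronger readings are tempting. A reader might infer that the design can never support a comparative claim; step 4 shows otherwise near 80 pairs. A reader might treat the missing power calculation as the defect; a study that only estimates does not need one. A reader might also infer that kit and sample type are confounded, since section 2.2.1 lists one kit for swab only and another for saliva only. But that section lists a third kit for both, and the assay rows in section 2.1.1 are redacted, so no such conclusion can be drawn.

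**Conclusion.** The point holds as a mismatch between the promised conclusion and the planned analysis. At the permitted minimum the conclusion is not supported: with all same-day swabs positive, perfect agreement leaves limits of 83.2% and −16.1 points. Near 80 pairs, a claim limited to detection may be reachable at a margin of about 10 points if discordance is low; at 5 points it is unlikely to succeed. These statements rest on assumed margins and discordance rates and on equal true detection in step 4.

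An unqualified claim of equal reliability would not follow even from a large sample of positives, because such a sample says nothing about false positives. A false-positive saliva result would count in saliva's favour in the difference.

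This should be fixed before testing, but it is not fatal: one summary sentence goes beyond an otherwise modest plan. The unclear entry wording is a side point. It matters because it decides who belongs in the denominator.

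**What to change.** 1. Reword the summary objective as estimating the agreement, and the difference in detection, between saliva and throat swab in PCR-confirmed participants. This fits the milder wording of sections 1.4, 2.1.1 and 3.
2. Specify the paired 2×2 table, the saliva-minus-swab difference in positivity with a paired-score 95% interval, and positive agreement (saliva-positive among swab-positive) with an exact 95% interval.
3. If a comparative claim is kept, limit it to detection in PCR-confirmed participants. Make it only if the lower limit of the difference clears a margin that the sponsor fixes before testing, and choose the minimum number of pairs for that margin with realistic discordance. The zero-discordance thresholds of 35 and 73 should not serve as sample sizes.
4. Reconcile the suspected-or-confirmed wording of sections 2.1.2 and 2.1.3 with the summary's requirement that participants be positive.

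Items 1, 2 and 4 cost protocol text and a little analysis, with no extra participants or samples. The price is a more modest conclusion if enrolment stops near 20. Item 3 costs more: it needs enrolment well above the minimum, and a 5-point claim would probably need more than the permitted 80.

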1. INTRODUCTION

Severe Acute Respiratory Syndrome Coronavirus 2 (SARS-CoV-2) has been identified as the cause of the pandemic outbreak of the coronavirus disease 2019 (COVID-19). Boehringer Ingelheim (BI) has launched a large-scale RT-PCR confirmation programme called COVID-19 Tests to counter the pandemic and safeguard public health. This dedicated health care measure was developed to complement the actions implemented by public health care to relieve the efforts of the health authorities.

The global pandemic COVID-19 is a reportable disease in most countries and local health authorities are monitoring the contacts of infected individuals to detect potential additional infections in order to prevent the spread. Contact tests generally depend on the presence of certain respiratory symptoms which coincide with the established risk criteria for increasing the probability of a positive nucleosides (RNA) result for SARS in swabs or sputum samples **[RKI 2020]**. It is therefore assumed that tests must be performed on as many individuals as possible in order to contain the pandemic situation. As such, the sampling method has become a critical factor, as it is more difficult to take swab samples than to collect saliva, and sampling must be optimised to allow more flexibility in obtaining samples for virus RNA identification, regardless of the availability of medical staff and testing centres. Furthermore, a method that could be performed at home and during quarantine will prevent the spread and reduce the biosafety risk in general.

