3. SAMPLE SIZE

There is no calculated sample size but rather a general attempt to directly compare swab samples versus saliva samples collected with Salivette® Cortisol in a participant, with a minimum of 20 to 80 participants.

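### The objective claims saliva is as reliable for identifying infection, but only SARS-CoV-2 positives are counted, so detection can be compared and specificity cannot.

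*Combined protocol and SAP*

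**What the plan says.** In the protocol summary, the objective is to demonstrate that saliva collection with the Salivette device "is as reliable as the use of throat swabs in sampling viral RNA for RT-qPCR and identifying SARS-CoV-2 infections". The entry for the number of participants reads "minimum of 20 and up to 80 participants who are positive for SARS-CoV-2". The main inclusion criterion there, labelled as applying to the pilot phase, is a PCR-confirmed diagnosis no more than 5 days old. The statistical methods entry promises a descriptive comparison of results and names no agreement measure, reference standard or margin.

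The body is looser about who is enrolled:

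- Section 2.1.2 (main diagnosis for admission): "Suspected or confirmed cases of SARS-CoV-2 infections (including COVID-19), confirmed with PCR within the past five days". This mentions suspected cases and then appears to require confirmation.
- Section 2.1.3 (inclusion criteria): "Suspected or confirmed SARS-CoV-2 infection by PCR within the past five days". This can be read as admitting people who are only suspected.
- Section 3 (sample size): "There is no calculated sample size but rather a general attempt to directly compare swab samples versus saliva samples", "with a minimum of 20 to 80 participants". Positivity is not restated.

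No section plans an uninfected group, a number of negatives, or a measure of specificity or negative agreement. Section 2.2 mentions specificity only as one reason for choosing the kits.

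**The concern.** Identifying infection reliably has two parts: finding RNA in infected people, and not reporting it in uninfected people. A sample counted only in positives bears on the first part alone. If saliva and swab perform alike in these participants, the objective as worded would let the report conclude equal reliability for identifying infection, although no uninfected person was planned to be tested.

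The Introduction encourages that wider reading, since it argues that "tests must be performed on as many individuals as possible in order to contain the pandemic situation". A reader could carry the conclusion over to people whose infection status is unknown, where false positives matter and this study would have no planned data on them.

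**Working it through.** **1. The plan's own figure.** There is nothing to reproduce. Section 3 says that no sample size was calculated, and the documents give no error rate, power, margin or expected detection rate. The 20 to 80 is a stated range.

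**2. What a sample of positives can identify.** Let N1 be the number of infected and N0 the number of uninfected participants, with Se and Sp the sensitivity and specificity of saliva.

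Expected saliva positives = N1 × Se + N0 × (1 − Sp).

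The summary gives N1 = 20 to 80 and N0 = 0, so the second term is zero and Sp drops out. The data are the same whether Sp is 0% or 100%.

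**3. What the paired table gives.** For N recently confirmed people, let a = both samples positive, b = swab only, c = saliva only, d = neither.

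- Swab detection rate = (a + b)/N
- Saliva detection rate = (a + c)/N
- Paired difference, saliva minus swab = (c − b)/N

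All three can be estimated. Eligibility rests on a PCR up to five days old, so a swab taken on the test day can be negative, and cells c and d need not be empty. Those people were still recently infected, so neither cell measures specificity.

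The reference also matters. Against the enrolment PCR the denominator is N; against the same-day swab it is a + b.

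**4. Precision of a detection rate.** Exact (Clopper-Pearson) 95% limits for x of n: the lower limit is the 0.025 quantile of Beta(x, n − x + 1), and the upper limit is the 0.975 quantile of Beta(x + 1, n − x). The values of n are the ends of the planned range; the values of x are illustrative.

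| Detected | Rate | Exact 95% interval |
|---|---|---|
| 20/20 | 100% | 83.2% to 100% |
| 19/20 | 95% | 75.1% to 99.9% |
| 18/20 | 90% | 68.3% to 98.8% |
| 80/80 | 100% | 95.5% to 100% |
| 76/80 | 95% | 87.7% to 98.6% |
| 72/80 | 90% | 81.2% to 95.6% |

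**5. Could suspected-only cases supply the missing part?** Suppose m of them prove negative and none is saliva-positive. The exact 95% upper limit for the saliva-positive proportion is 1 − 0.025^(1/m). The values of m are assumptions; the documents give none.

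- m = 5: 1 − 0.025^(1/5) = 0.522
- m = 10: 1 − 0.025^(1/10) = 0.308
- m = 20: 1 − 0.025^(1/20) = 0.168

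Twenty negatives would be a quarter of the largest planned sample (20/80 = 25%), and the upper limit would still be about 17%. If negative means only swab-negative, a saliva positive could also be a true detection, so even this proportion would not be a clean false-positive rate.

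**6. What the broader claim would need.** If every negative agrees, a 95% lower limit of at least L for specificity needs m = ln(0.025)/ln(L), rounded up: 17 for L = 80%, 36 for 90% and 72 for 95%. These targets are assumptions.

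**The case against.** The strongest case for the plan is that it compares ways of collecting a sample and does not evaluate a new assay. Section 2.1.1 speaks of establishing saliva collection. The failure that the summary and section 1.3 name is the false negative, which a sample of positives addresses directly. The kits carry CE marking and each run has a negative control (sections 2.2 and 2.2.1). The work is described as a pilot with descriptive statistics, and the plan nowhere promises a figure for specificity or overall agreement.

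Much of this stands. The focus on false negatives is legitimate, and the narrowed objective keeps it in full. Kit quality, however, does not establish specificity in saliva. Section 1.2.1 describes the cobas test as validated for swab samples, and section 2.2.1 lists cobas for swabs only, TaqPath for Salivette only and Kylt for both. A descriptive pilot also sits badly with an objective to demonstrate equal reliability in identifying infection.

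A reader might go further and infer that false positives would dominate the errors in mass testing. The documents do not support that: they give no prevalence or accuracy figures, the mass-testing sentence is background, and section 1.1 says regular testing can be applied only to selected groups. A reader might also infer that overall agreement must nearly equal positive agreement, but a same-day swab can be negative in a recently confirmed person.

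**Conclusion.** The point holds as a mismatch between the objective and the sample. With 0 uninfected participants planned, saliva specificity and the false-positive rate cannot be estimated. Each sample type's detection rate and the paired difference can, with exact intervals for a 95% rate running from 75.1-99.9% (19/20) to 87.7-98.6% (76/80). The data stay useful; it is the stated objective that exceeds them.

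Three assumptions carry this. The summary's count of positives describes the intended sample; sections 2.1.2, 2.1.3 and 3 leave that unclear. A PCR confirmation within five days marks true infection. Any suspected-only negatives would be incidental, since none is planned.

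It would be too strong to say that saliva is likely to give false positives, because nothing in the documents points either way. It would also be too strong to say that only positive agreement can be estimated, or that narrowing is the sole remedy. A planned negative group would also resolve the mismatch.

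**What to change.** 1. Restate the objective, and the conclusion to be drawn, as detection of viral RNA by saliva versus throat swab in people whose infection was confirmed by PCR within the past five days.
2. Name the enrolment PCR as the reference. Report each sample type's detection rate with an exact 95% interval, the full paired 2×2 table with both discordant counts, and the paired difference.
3. State that no specificity or general diagnostic-accuracy claim will be made.
4. Reconcile the summary with sections 2.1.2, 2.1.3 and 3 on whether suspected-only cases are enrolled. If they are, tabulate them separately and draw no accuracy conclusion from them.

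The cost is wording and one results table, with no added participants or samples. The downside is a narrower headline claim. If the sponsor prefers to keep the broader objective, a planned negative group of justified size is needed, which is not a cheap change.
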